| Number(s): | |
| Other research reference | |
| number(s) (if applicable) | |
| Full (Scientific) title | Extended follow up of the TARGIT-A trial |
| Health condition | Early breast cancer |
| Study Type | Observational cohort study |
| Target sample size | 714 |
| | |
| STUDY TIMELINES | |
| Study Duration/length | Five years |
| Expected Start Date | 01 January 2018 |
| End of Study definition and | Follow-up information on all patients to at least 10 years. |
| anticipated date | |
| FUNDING & Other | |
| Funding | NIHR HTA |
| Other support | None |
| STORAGE of SAMPLES | No samples will be collected. |
| KEY STUDY CONTACTS | |
| Chief Investigator | [name] [name] MBBS MS DNB FRCS PhD |
| | Professor of Surgery and Oncology, |
| | Division of Surgery and Interventional Science, |
| | University College London |

KEY ROLES AND RESPONSIBILITIES

SPONSOR: The sponsor is responsible for ensuring before a study begins that arrangements are in place for the research team to access resources and support to deliver the research as proposed and allocate responsibilities for the management, monitoring and reporting of the research. The Sponsor also has to be satisfied there is agreement on appropriate arrangements to record, report and review significant developments as the research proceeds, and approve any modifications to the design.

FUNDER: The funder is the entity that will provide the funds (financial support) for the conduction of the study. Funders are expected to provide assistance to any enquiry, audit or investigation related to the funded work.

CHIEF INVESTIGATOR (CI): The person who takes overall responsibility for the design, conduct and reporting of a study. If the study involves researchers at more than once site, the CI takes on the primary responsibility whether or not he/she is an investigator at any particular site.

The CI role is to complete and to ensure that all relevant regulatory approvals are in place before the study begins. Ensure arrangements are in place for good study conduct, robust monitoring and reporting, including prompt reporting of incidents, this includes putting in place adequate training for study staff to conduct the study as per the protocol and relevant standards.

The Chief Investigator is responsible for submission of annual reports as required. The Chief Investigator will notify the RE of the end of the study, including the reasons for the premature termination. Within one year after the end of study, the Chief Investigator will submit a final report with the results, including any publications/abstracts to the REC.

PRINCIPAL INVESTIGATOR (PI): Individually or as leader of the researchers at a site; ensuring that the study is conducted as per the approved study protocol, and report/notify the relevant parties – this includes the CI of any breaches or incidents related to the study.

Extended follow up of the TARGIT-A trial - Protocol

IRAS No: 236431

KEY WORDS

TARGIT IORT, TARgeted Intraoperative radiotherapy, breast conserving therapy, lumpectomy, wide local excision, randomised clinical trial, follow up.

LIST OF ABBREVIATIONS

AE Adverse Event
AR Adverse Reaction
CI Chief Investigator
CRF Case Report Form

CRO Contract Research Organisation
CTA Clinical Trial Authorisation

CTIMP Clinical Trial of Investigational Medicinal Product

DMC Data Monitoring Committee
DSUR Development Safety Update Report

EC European Commission
EMEA European Medicines Agency

EU European Union

EUCTD European Clinical Trials Directive
EudraCT European Clinical Trials Database

EudraVIGILANCE European database for Pharmacovigilance

GAFREC Governance Arrangement for NHS Research Ethics

GCP Good Clinical Practice

GMP Good Manufacturing Practice
HES Hospital Episode Statistics
HTA Human Tissue Authority
IB Investigator Brochure
ICF Informed Consent Form

IDMC Independent Data Monitoring Committee

IMP Investigational Medicinal Product

IMPD Investigational Medicinal Product Dossier

ISF Investigator Site File

ISRCTN International Standard Randomised Controlled Trials Number

MA Marketing Authorisation

MD Medical Device

MHRA Medicines and Healthcare products Regulatory Agency

MS Member State

Main REC Main Research Ethics Committee

NHS R&D National Health Service Research & Development

ONS Office for National Statistics
PDS Personal Demographics Service

PI Principal Investigator

PIS Participant Information Sheet

QA Quality Assurance
QC Quality Control

RCT Randomised Clinical Study
REC Research Ethics committee
SAR Serious Adverse Reaction

Extended follow up of the TARGIT-A trial - Protocol

IRAS No: 236431

SAE Serious Adverse Event
SDV Source Data Verification
SOP Standard Operating Procedure

1 INTRODUCTION

Breast cancer remains the commonest female malignancy and its incidence continues to rise. The common conventional treatment of early breast cancer involves surgical excision of the tumour, surgery to the axillary lymph nodes. This breast conserving surgery needs to be followed by external beam radiotherapy given over several weeks of daily treatments, given with the intention of reducing the rate of further cancer developing within the operated breast. Whilst this is an effective treatment with a low rate of local recurrence of cancer, our own laboratory work and its clinical correlation has suggested that radiation to the whole breast may not be necessary in all cases and radiotherapy to the tissue only around the tumour within a risk-adapted approach may be as effective.

The TARGIT-A randomised clinical trial, compared a risk-adapted approach with use of single dose targeted intra-operative radiotherapy (TARGIT IORT) vs. conventional external beam radiotherapy (EBRT) given as a daily course over 3 to 6 weeks.

The initial and 5 year results have been published^{5,6} and found that TARGIT-IORT is non-inferior to EBRT.

For the patients, the biggest benefit of having TARGIT-IORT during their lumpectomy procedure, under the same anaesthetic, is that they complete their local treatment in one session and with lower toxicity.

For any healthcare system including the NHS, TARGIT-IORT has been shown to be cost effective and incurs a lower overall cost to the NHS. It also reduces the journey times for patients who would otherwise need to travel, on average, 730 miles for their EBRT treatment.

The recruitment in the trial was completed in June 2012. This extended follow up study enables collection of longer term outcomes by direct patient contact and by data from national records such as the Office for National Statistics (ONS).

2 BACKGROUND AND RATIONALE

The TARGIT-A randomised clinical trial, compared a risk-adapted approach with use of single dose intraoperative radiotherapy vs. conventional radiotherapy. The biological and clinico-pathological arguments^{1, 2} for avoiding unnecessary treatment to the whole breast are as follows: In large studies of breast conserving therapy more than 90% of early breast recurrences have been found to occur at the site of the original primary tumour site. This is true whether or not radiotherapy is given and whether or not the margins are involved. Furthermore, when detailed examination of mastectomy specimens are performed using radiological-histological correlational methods, small additional invasive or in-situ cancer foci are found in over 60% of patients, with 80% of these situated remote from the index quadrant. The relative distribution of primary tumour and these occult foci in the four breast quadrants is significantly different. Thus, these occult cancer foci probably remain dormant and do not in general give rise to local recurrence, which more probably develops in the tissues that surround the primary tumour- and it is solely this area that may need radiation.

In the TARGIT-A trial, the experimental arm used the targeted intraoperative radiotherapy (TARGIT) technique using the Intrabeam device to give radiotherapy to the tissues around the tumour, during the lumpectomy procedure. The control arm received whole breast external beam radiotherapy given according to local policy, usually 40 to 50 Gy in 15 to 25 fractions, with a boost to the tumour bed. The technique of giving targeted intraoperative radiotherapy (TARGIT) using INTRABEAM™ (now manufactured by Carl Zeiss Surgical, Oberkochen, Germany) was developed in University College London in collaboration with the specialised manufacturers. It allows the patient to receive a single fraction of radiotherapy as soon as the primary tumour is excised, during the same anaesthetic¹-⁴. Advantages of this approach include: delivering

Extended follow up of the TARGIT-A trial - Protocol IRAS No: 236431

the radiation immediately, ensuring the radiation is delivered to the tumour bed under direct vision, thus avoiding a "geographical miss"; and decreased costs to the healthcare providers and patients.

INTRABEAM™ uses a mobile, miniature x-ray generator powered by a 12-volt supply. Accelerated electrons strike a gold target at the tip of a 10 cm long drift tube with a diameter of 3 mm, resulting in the emission of low-energy x-rays (50 kV) in an isotropic dose distribution around the tip. The irradiated tissue is kept at a fixed, known distance from the source by spherical applicators to ensure a more uniform dose distribution. The tip of the electron drift tube sits precisely at the epicentre of a spherical plastic applicator, the size of which is chosen to fit the cavity after the tumour is excised. Using this method, the walls of the tumour cavity are irradiated to a biologically effective dose (20 Gy to the tissue in contact with the applicator) that rapidly attenuates over a distance of a few centimetres. As a result, vital organs (such as the heart and the lungs) are spared. Since these are soft x-rays, the biologically effective dose attenuates rapidly so that the highest radiation dose is received by tissue nearest the primary tumour, and a much lower dose by the skin and other normal tissues. It also means that there is no need for a specialised operation theatre and TARGIT can be given in a standard unmodified operating theatre with no need for lead shielding other than a mobile shield to protect the equipment operators.

The published results^{5,6} of the TARGIT-A trial show that compared with conventional external beam radiotherapy given over several weeks, TARGIT given at the time of lumpectomy within a risk-adapted approach achieves much the same results in terms of breast cancer control (locally and systemically). Interestingly, TARGIT was found to have a significantly lower mortality from causes other than breast cancer due to fewer deaths from cardiovascular causes and other cancers.

Although the current results are convincing enough for the treatment to be adopted worldwide (over 20,000 women have now had this treatment in about 300 centres in 35 countries), it is essential that all the 3451 patients are followed up over a longer period of time and data analysed as per the original protocol.

This extended follow up study will enable timely recording of additional local recurrences and deaths. With a higher number of events, it would be possible to perform meaningful subgroup analysis using predictive factors such as hormone receptors (available data suggests that these have a predictive value), tumour grade and lymph node involvement that would allow fine tuning of patient selection criteria. Furthermore the effect on non-breast-cancer and overall mortality will also be ascertained.

We expect these new data will significantly influence wider and enthusiastic adoption of this approach that will be greatly welcomed by patients. As a large proportion of such patients are screen-detected, their overtreatment would be avoided by such adoption.

3 **OBJECTIVES**

The objective of this protocol is to obtain follow-up information including details of diagnosis and treatment of any disease relapse, other cancer incidence, or death (including the cause of death) in all enrolled patients as per the TARGIT A Trial protocol.

4 STUDY DESIGN

This protocol gives the details of the additional approaches to the follow up of patients randomised in the TARGIT-A Trial. The design of the TARGIT-A trial is given in the appendix.

5 **STUDY SCHEDULE**

The study has been divided into two Work Packages.

Work Package 1: Continue to gather efficacy, safety and follow-up data to year 10, all centres, using the current methods as per protocol.

Aim and rationale

The latest analysis of the TARGIT-A trial, includes a very large number of patients (1222) with a median follow up of 5-years and our analysis suggests that the results remain the stable for cohorts of patients with increasing periods of follow up. However, for the whole trial, the median follow up is 2.6 years, and one the barriers to widespread adoption of the new treatment could be the perception that we should have a 5-year follow up of all the patients in the trial – this will mean that a substantial number will also have a 10 year follow-up, a milestone that is now considered essential in many trials. Importantly, follow up to 10 years was stipulated in the original protocol. The work package WP1 will deliver this.

Primary & secondary objectives

To evaluate in the longer term, primary outcome i.e., local recurrence in the conserved breast and secondary outcomes of the main trial, including complications/side effects, breast cancer and non-breast-cancer survival.

Brief description of methods and statistical analysis

All patients recruited in the trial (n=3451) from 33 centres in 11 countries will be followed up as defined in the original protocol (6 monthly for 5 years and annually thereafter until 10 years). The analysis of the updated database will be directed by a statistical analysis plan (SAP) appended to this application. The higher number of events with longer follow up will also give more robustness to the planned subgroup analysis (e.g., effect of hormone receptor status) to inform further individualization of the treatment. Analysis will be performed as per the submitted Statistical Analysis Plan that has been signed off by the Chair of the DMC ([name]). As usual, any modifications of the SAP, based on new information such as data from other trials and biological insights, will be finalized and signed off BEFORE unblinding of the database. The current plan is to analyse as per the two pre-pathology and post-pathology strata as well as subgroup analysis as per hormone receptor status and hormone therapy. Multivariate analysis will also be performed for assessing the predictive value of other tumour and patient factors such as age, tumour size, grade, lymph node status, margins, lymphovascular invasion, time since randomization, etc.

Detailed Methods of Data Collection

With many trusts in the UK stopping clinical follow up after 5 years, it will be more effective to use different follow approaches for obtaining follow up information. All follow-up data will be chased via site (hospital) and directly from the patient every 6 months for the first five years, and then annually thereafter. After ten years all follow up will be directly through patient contact. A case report form (CRF) has been specifically designed for direct-to-patient contact. As in the previous analysis, an independent reviewer ([name]) will specifically deal with assessment of cause of death supported by a cause-of-death committee. Case record forms, death certificates and case notes will be used to ascertain the cause of death, blinded to the randomisation arm. Special attention will be paid to cardiovascular and other-cancer mortality. CRFs will be sent out at scheduled timepoints. Should a CRF fail to arrive at SITU after 6 weeks, a reminder will be sent out. For the 6 monthly CRFs, only one reminder will be sent, for annual CRF, two reminders will be sent 6 weeks apart. As per protocol, follow-up (clinical examination and mammogram) will continue annually at least until the 10th year after randomization. Annual mammograms are normally performed as part of usual care for 10 years following breast cancer surgery. All follow-up data will be collected via site (hospital) and directly from the patient every 6 months for the first five years, and then annually thereafter. In addition to contacting sites, this extension will enable us to (i) contact patients directly (following appropriate permissions being obtained), and (ii) obtain information on new primary cancers and death from the ONS. Should either of these methods reveal anything other than "healthy" follow-up, site staff will be contacted directly to obtain further information.

Work Package 2: Collect death & new primary cancer data from UK patients through ONS.

Collection of death & new primary cancer data from UK patients through ONS will help improve the completeness of the data, and will support WP1.

Detailed Methods of Data Collection

All UK patients will be registered with the Office for National Statistics (ONS), for cohort event notifications. These reports will be sent quarterly and will show Exits from the NHS, Embarkations, Re-entries into the NHS, Deaths and new primary cancer registrations. Cause of death reports will be requested for each patient.

Statistical considerations

The original sample size of 2232 was powered at 80% to prove non inferiority with a 2.5% absolute difference (the non-inferiority margin) in local recurrence. A two-year extension to accrual means that the follow-up of 3451 patients for 5 years has increased the power to 92.6% (based on the same original assumptions). In addition, we have found a borderline-significant overall survival advantage with TARGIT with a hazard ratio of 1.43 (p=0.099). We would need 243 events to have statistical power to demonstrate superiority in overall survival with 95% confidence. We expect to record this number in the proposed follow up period.

Study Activities

See Figure for an illustration of the patient progress though the study.

The clinical trials unit (SITU) will send to each Principal Investigator (PI) a list of patients who meet the eligibility criteria as per information held on the database (alive, not withdrawn consent). The PI will review the list to ensure the information is up-to-date. The PI will make the initial approach to the patient. He/she will send the approved letter (on local letterhead) to each patient, together with the participant information leaflet, consent form, contact details form, and follow-up (questionnaire) form. If the patient has any questions, she can telephone the office of the PI (contact details will be provided), or have a face-to-face discussion at her next clinic visit.

[figure not shown]
If the patient consents to take part in the study, she must complete the consent form, contact details form, and follow-up (questionnaire) form. These should be sent to SITU by post in the pre-paid envelope provided. One copy of the consent form will be returned to the patient, one copy will be sent to the PI, and the original will remain in SITU.

If the patient explicitly states that she refuses to participate, no further contact will be made. If the patient does not reply, the PI will be asked to send a reminder to the patient. If no contact is made after three attempts, no further contact will be made.

Patients who have consented to be in the study will be "flagged" with administrative databases such as ONS and the Cancer Registry. In addition, the patient will be contacted annually directly by SITU and asked to update the contact details form (if necessary), and complete a follow-up (questionnaire) form, and return by post in the pre-paid envelope provided. Patients will be followed up until death or withdrawal of consent. Patients can refuse consent at any time by contacting either SITU or the PI, in which case no further contact will be made.

Data will be added to two databases. One database will contain identifiable data (patient name and contact details), the other will contain pseudonymised (de-identified) data and will eventually be sent to the Trial Statistician for analysis. The information on the databases will be linked by a unique, anonymous identifier.

TARGIT Direct - Patient Pathway

Extended follow up of the TARGIT-A trial - Protocol

IRAS No: 236431

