9 STATISTICAL METHODS

This protocol only relates to continuing collection of follow up information from patients already in the TARGIT-A trial. Formal statistical analysis will be performed as per the original TARGIT-A trial. In brief, analysis will be performed as per the submitted Statistical Analysis Plan (SAP) that has been signed off by the Chair of the DMC ([name]). As usual, any modifications of the SAP, based on new information such as data from other trials and biological insights, will be finalized and signed off BEFORE unblinding of the database. The current plan is to analyse as by pre-pathology and post-pathology strata as well as subgroup analysis as per hormone receptor status and hormone therapy. Multivariate analysis will also be performed for assessing the predictive value of other tumour and patient factors such as age, tumour size, grade, lymph node status, margins, lymphovascular invasion, time since randomization, etc.

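### The planned subgroup by hormone therapy may not be a randomised comparison, because therapy can be chosen after allocation with the arm known

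*Protocol*

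**What the plan says.** Two places in the protocol fix the same plan. Section 5 (Work Package 1, brief description of methods and statistical analysis) lists "subgroup analysis as per hormone receptor status and hormone therapy" after the analysis by pathology stratum. Section 9 repeats it: "The current plan is to analyse as by pre-pathology and post-pathology strata as well as subgroup analysis as per hormone receptor status and hormone therapy". Neither says whether hormone therapy means indicated, prescribed, started or received. Neither ties it to a time before or after randomisation, and neither adds a caution about how the comparison may be read. Section 5 also says that the planned subgroup analysis is meant "to inform further individualization of the treatment", with receptor status as its example.

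On timing and masking, section 2 says that the experimental arm used a technique "to give radiotherapy to the tissues around the tumour, during the lumpectomy procedure". On the other side, "The control arm received whole breast external beam radiotherapy given according to local policy", which section 1 describes as a daily course over 3 to 6 weeks. The only blinding to arm that the protocol states is for death review: section 5 says that records "will be used to ascertain the cause of death, blinded to the randomisation arm".

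**The concern.** A subgroup treatment effect keeps the protection of randomisation when the subgroup is fixed before allocation or cannot be affected by it. Receptor status meets that condition. Hormone therapy received need not. In the pre-pathology stratum, the stratum's name and the delivery of treatment at lumpectomy imply that patients were allocated before final pathology. A hormone-therapy decision that draws on that pathology then comes after allocation and can be influenced by it.

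If such influence differs by prognosis, users in one arm are not comparable with users in the other, and the same holds for non-users. The two subgroups can then show different treatment effects when there is none in either. Because the planned subgroup work is meant to guide individual treatment, a false interaction could be read as a reason to treat users and non-users differently.

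**Working it through.** The protocol gives no figure to reproduce here, and no uptake or recurrence rates by hormone therapy. The check is therefore an illustration on assumed inputs, followed by a range.

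**Formula.** For risk classes k with share p_k, recurrence risk r_k (the same in both arms) and uptake u_ak in arm a, recurrence among users is Σ p_k·u_ak·r_k ÷ Σ p_k·u_ak. For non-users, replace u_ak by 1 − u_ak. The arm enters only through u_ak. If uptake is equal in both arms within every risk class, the arm difference in each subgroup is exactly zero.

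**Main illustration (all inputs assumed).** 30% of patients are high risk with 10% recurrence, and 70% are low risk with 3%. Radiotherapy arm and hormone therapy have no effect on recurrence. High-risk uptake is 90% in both arms. Low-risk uptake is 60% with EBRT and 75% with TARGIT. The true rate in both arms is 0.30 × 10 + 0.70 × 3 = 5.1%.

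| Subgroup | EBRT | TARGIT | TARGIT − EBRT |
|---|---|---|---|
| No hormone therapy | (0.03×10 + 0.28×3)/0.31 = 3.68% | (0.03×10 + 0.175×3)/0.205 = 4.02% | +0.35 points |
| Hormone therapy | (0.27×10 + 0.42×3)/0.69 = 5.74% | (0.27×10 + 0.525×3)/0.795 = 5.38% | −0.36 points |

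The false interaction is 0.35 + 0.36 = 0.71 points.

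**Range (second set of assumptions).** There are two equal classes with risks of 2% and 8% and again no treatment effect. Uptake is given as low risk/high risk, one arm versus the other.

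| Uptake | Difference, users | Difference, non-users |
|---|---|---|
| 60/80 vs 60/80 | 0.0 | 0.0 |
| 60/80 vs 70/75 | 5.10 − 5.43 = −0.33 | 4.73 − 4.00 = +0.73 |
| 50/90 vs 70/75 | 5.10 − 5.86 = −0.75 | 4.73 − 3.00 = +1.73 |

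In the last row, overall uptake is (50 + 90)/2 = 70% against (70 + 75)/2 = 72.5%. Similar overall uptake therefore does not rule out the bias. What matters is uptake within prognostic level.

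**Scale against chance.** Take the main illustration with 3451 patients, an assumed 1:1 split and simple proportions. The four cells hold about 535, 354, 1191 and 1372 patients. The variances, each rate × (100 − rate)/n in squared points, are 0.66 + 1.09 + 0.45 + 0.37 = 2.58, which gives a standard error of about 1.6 points for the interaction. The 0.71-point artefact is 0.71/1.6 = 0.44 of that.

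**The case against.** The strongest case on the other side has four parts.

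- **The subgroup may be harmless as defined.** The protocol text does not say when hormone therapy was decided, and the SAP, not available here, may define the subgroup by indication. In the post-pathology stratum the decision may precede randomisation. This stands. A reader might infer that these comparisons are certainly not randomised, but the documents support only that they may not be.
- **Knowing the arm does not prove that uptake differed.** This also stands: with equal uptake in each risk class the bias is zero. The protocol never uses the term open-label, although masking is implausible given the two treatments.
- **Subgroup definitions belong in the SAP.** This is only partly an answer. The protocol itself names a treatment as a subgrouping variable, twice, without restriction.
- **The bias is modest.** In the main illustration it is 0.35/2.5 = 14% of the 2.5-point margin within a subgroup. Setting the 0.71-point interaction against that margin would mislead, because the margin concerns the arm difference in local recurrence.

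Two further readings go beyond the text. The section 2 sentence on refining patient selection names receptors, grade and nodes, not hormone therapy. A reader might also infer that listing time since randomization among the factors ("age, tumour size, grade, lymph node status, margins, lymphovascular invasion, time since randomization, etc") conditions on the future. That would be so only if observed follow-up were entered as an ordinary covariate, which the text does not say. Section 5 compares cohorts by length of follow-up, and section 8 gives accrual from March 2000 to June 2012. An entry-cohort or treatment-by-time meaning is therefore at least as natural, and both are legitimate. I raise no objection on that item.

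**Conclusion.** The point holds for hormone therapy, in conditional form. As written, both sections allow a treatment-effect subgroup defined by a decision that can follow allocation and be made with the arm known. The resulting comparison may then be confounded by prognosis.

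The size is unknown from the documents. The main illustration gives about 0.35 points in each subgroup, and the second set of assumptions gives 0.3 to 1.7 points. All of these rest on assumed uptake that depends on arm within risk level, and all vanish without it. The defect should be corrected because the remedy is nearly free. It does not touch the primary comparison or the receptor-status subgroup.

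**What to change.** Make the same change in section 5 (Work Package 1) and section 9, and carry it into the SAP if the SAP has the same wording:

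- Keep hormone receptor status as the subgroup, tested by a treatment-by-receptor interaction.
- Remove hormone therapy received as a treatment-effect subgroup, or define the subgroup by an indication fixed before randomisation.
- Report hormone-therapy uptake descriptively by arm, preferably also within receptor status and pathology stratum, since overall uptake can hide differences.
- Label any analysis by receipt as exploratory and non-randomised.

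The cost is a line of text in two places and the loss of a formal treatment effect by hormone-therapy use. No new data are needed. Both sections require SAP changes to be signed off before unblinding, so the wording should be settled by then.
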